8.0 Statistical Considerations

The sample size of 110 for the RCT is based on our Phase 1 pretest results and an a priori power analysis for a multiple regression with 4 predictors of PrEP adherence, which was conducted to determine a sample size with a power of at least 90% with a two-sided alpha level of .05. The desired minimum sample size was 92 participants (Rosner, 2010). In the event of 20% attrition, we added 20% additional participants to the sample, and set 110 as the total sample size. Therefore, even if the study encounters diminished recruitment or greater post-recruitment attrition, it should still be possible to detect moderate effects.

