Analysis plan:

Data Analysis: Analyses will be performed using SPSS version 22 to run diagnostics (tests for normality, multicollinearity, heteroscedasticity) to assess violations of analytic assumptions, univariate statistics, bivariate tests, and multivariate linear regression. Because study retention may be influenced by preconditions, t-tests or Wilcoxon test will be used to compare intervention group and control group on all T1 variables. T- tests can be used for normal distribution while Wilcoxon test can be used in skewed distribution. Implications of significant differences will be discussed. Based on the intent to treat approach, missing T2 data will be imputed to retain all participants in analyses. We will include all participants who provide informed consent and engage in the T1 assessment, regardless of what portion of the assigned treatment or control protocol is completed. Data will be imputed using multiple imputation for participants who fail to complete the T2 (posttest) assessment.

Sensitivity analyses will explore the implications of the imputation methods employed (e.g., multiple imputation, propensity score matching). Post- recruitment attrition (loss of potential participants who were recruited but failed to engage in any assessments or part of the treatment or control protocol) will be explored in all discussion and implications of study findings. The following series of regressions will assess study hypotheses.

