Hypothesis 1: Exposure to mhealth intervention will result in significant improvement in PrEP adherence compared to the control group. We will firstly examine the distribution of all variables and their correlations. Where two similar variables are correlated at $r>0.4$, 1 variable will be selected for inclusion in regression models to avoid collinearity (see Patel et al., 2016). We will employ multivariate linear regression to estimate the association between the intervention and PrEP adherence. In order to compare the difference of PrEP adherence (after 12 weeks) between intervention group and control group, the first regression model will only include the dichotomous treatment variable (intervention group versus control). Based on the first model, the second regression model will add three confounders (three demographic variables: age, education, and income) to compare the gaps after controlling for age, education and income level. Based on the second model, besides the 3 confounders, the third regression model will add an interaction term, the dichotomous treatment variable and the dichotomous intervention variable (before the intervention vs after) and their interaction. The coefficient of the interaction term will be the difference between the increase in intervention group and the increase in control group.

Hypothesis 2: The impact of intervention on the primary outcome will be mediated through key factors, i.e. increased PrEP self-efficacy, increased PrEP knowledge, increased intention to follow PrEP guidelines, and reduced stress burden. To test

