the mediation effect, the following three regressions will be conducted. First, we will set PrEP adherence as the dependent variable, demographic variables and dichotomous treatment variable and other independent variables as the independent variables. Second, we will set PrEP adherence as the dependent variable, and each of the four mediators as the independent variable. Third, we will set the dichotomous treatment variable as the dependent variable and each of the four mediators as the independent variables. The coefficients of the three regressions will show the mediation effects. Time on PrEP will be examined as a potential moderating variable, including the potential for moderated mediation in which mediators may become significant only at certain levels of the time since starting PrEP. Results will be interpreted via the standard interpretation of a sequence of regression models (Aneshensel, 2002; Baron & Kenny, 1986) to determine whether these variables mediate or partially mediate intervention effects, and the extent to which time on PrEP moderates these relationships.

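### None of the three Hypothesis 1 models is named as the deciding one, and baseline adherence is a covariate in none of them

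*SAP*

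**What the plan says.** The SAP's Data Analysis paragraph introduces the models with "The following series of regressions will assess study hypotheses". Under Hypothesis 1 there are three:

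- **Model 1:** "the first regression model will only include the dichotomous treatment variable (intervention group versus control"), with adherence after 12 weeks as the outcome.
- **Model 2:** "the second regression model will add three confounders (three demographic variables: age, education, and income").
- **Model 3:** the same three demographic variables, treatment, a before/after indicator and their product. Of this model the SAP says "The coefficient of the interaction term will be the difference between the increase in intervention group and the increase in control group".

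A screening rule comes before all three: where two similar variables correlate above 0.4, "1 variable will be selected for inclusion in regression models to avoid collinearity".

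The Measures section of the SAP describes the primary outcome as a T1-to-T2 comparison and collects the 3-item adherence measure at both times. On the analysis set the SAP states: "We will include all participants who provide informed consent and engage in the T1 assessment". The Demographic and Control Variables paragraph lists age, education, income and time on PrEP, but not T1 adherence.

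Section 8.0 of the protocol bases the sample size on "an a priori power analysis for a multiple regression with 4 predictors of PrEP adherence, which was conducted to determine a sample size". The SAP's power paragraph says the same. Neither lists the predictors.

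**The concern.** There are two linked gaps.

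**No deciding test.** Three coefficients could each be reported as the answer to Hypothesis 1, and no rule chooses among them. The hints conflict. The primary outcome description leans to Model 3. The count of four predictors in the power statement matches Model 2 (treatment, age, education, income). It could equally refer to Hypothesis 2, where "we will set PrEP adherence as the dependent variable, and each of the four mediators as the independent variable". It does not match Model 3, which has six terms. The same data could therefore support the hypothesis under one planned model and not under another. If significance in either Model 2 or Model 3 were accepted, the stated two-sided 0.05 would not hold.

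**Precision not fully used.** T1 adherence would normally be expected to be among the better predictors of 12-week adherence, and it is already collected. Models 1 and 2 leave it out. Model 3 uses it as an outcome record and keeps a free treatment main effect, so it estimates a difference in differences and does not reach the precision of baseline adjustment.

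**Working it through.** **Inputs from the documents.** Minimum N = 92; total 110, 55 per arm; 90% power; two-sided 0.05; 20% attrition. Taking 20% off 55 leaves 44 per arm.

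**Assumptions, because the documents give no figure.** Standardised effect d = 0.5 or 0.65; T1-T2 correlation ρ = 0.3, 0.5 or 0.7; equal SDs at both times; normal outcome; demographic covariates that explain nothing; income entered as a single score; Model 3 analysed with the pairing of T1 and T2 respected. The SAP states no within-person term for Model 3. That is a separate matter.

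**Step 1: the plan's own figure.** N = 92 cannot be reproduced without an effect size, but it can be inverted. For 90% power on one coefficient among four predictors (residual df 92 − 5 = 87), the noncentral F gives f² = 0.117. With equal arms, d = 2√f² = 0.68. Read instead as the 4-df overall test, it gives f² = 0.177. The step to 110 is 92 × 1.2 = 110.4.

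**Step 2: relative variance of the treatment effect.**

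- Models 1 and 2 (12-week outcome only): 1
- Model 3 (difference of paired changes): 2(1 − ρ)
- T1-adjusted: 1 − ρ²

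The gaps are 1 − (1 − ρ²) = ρ² and 2(1 − ρ) − (1 − ρ²) = (1 − ρ)². Neither can be negative, so the direction does not depend on ρ. Models 2 and 3 change rank at ρ = 0.5.

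| | ρ = 0.3 | ρ = 0.5 | ρ = 0.7 |
|---|---|---|---|
| Models 1 and 2 | 1 | 1 | 1 |
| Model 3 | 1.40 | 1.00 | 0.60 |
| T1-adjusted | 0.91 | 0.75 | 0.51 |
| Extra participants Model 2 needs to match, 1/(1 − ρ²) − 1 | 10% | 33% | 96% |
| Extra participants Model 3 needs to match, 2/(1 + ρ) − 1 | 54% | 33% | 18% |

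**Step 3: power.** Noncentral t with noncentrality d/√(2v/n), where v is the relative variance and n the number per arm, and with covariate degrees of freedom removed. Entries are for ρ = 0.3 / 0.5 / 0.7.

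| d, n per arm | Model 2 | Model 3 | T1-adjusted |
|---|---|---|---|
| 0.5, 44 | 64.0% | 50.0 / 64.0 / 84.9% | 68.1 / 76.3 / 90.1% |
| 0.5, 55 | 73.8% | 59.3 / 73.8 / 91.8% | 77.7 / 85.1 / 95.3% |
| 0.65, 44 | 85.4% | 72.1 / 85.4 / 97.3% | 88.5 / 93.6 / 98.8% |
| 0.65, 55 | 92.2% | 81.4 / 92.2 / 99.2% | 94.3 / 97.4 / 99.7% |

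Simulation with three independent covariates (20,000 trials per setting) gives powers up to 2.2 points lower, because of chance covariate imbalance. Each single model rejects a true null in 4.7-5.2% of trials.

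**Step 4: effect detectable with 90% power at N = 92 (46 per arm).** Model 2: d = 0.68. Model 3: 0.81 / 0.68 / 0.53. T1-adjusted: 0.65 / 0.59 / 0.49.

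**Step 5: how often Models 2 and 3 disagree on significance (same simulation).**

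| d, n per arm | ρ = 0.3 | ρ = 0.5 | ρ = 0.7 |
|---|---|---|---|
| 0.5, 44 | 31.6% | 32.1% | 34.0% |
| 0.5, 55 | 29.6% | 27.2% | 26.2% |
| 0.65, 44 | 24.1% | 19.3% | 16.3% |
| 0.65, 55 | 17.8% | 11.8% | 8.8% |

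At d = 0.5 and 55 per arm, only Model 2 is significant in 21.9 / 13.6 / 3.7% of trials and only Model 3 in 7.7 / 13.7 / 22.4%.

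**Step 6: error rate if either test is accepted.** With no true effect and 46 per arm, claiming success when either the 12-week contrast or the paired-change contrast is significant gives 8.7% (ρ = 0.3) to 9.5% (ρ = 0.7) false positives in simulation.

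**The case against.** The strongest reply is that Model 3 is already primary in all but name. Hypothesis 1 is worded as an improvement relative to control, the models build up to Model 3, its interaction is the only coefficient the SAP interprets, and the primary outcome is described as a T1-T2 comparison. This is a fair reading, but it stays an inference: no sentence names the model, and a power statement with four predictors does not describe a six-term model. Even if it is granted, Model 3 is less precise than T1 adjustment at any ρ below 1.

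The size of the gain is also open to challenge, and part of this stands. The 96% and 54% figures compare with the weaker planned model at that ρ. Against the better of Models 2 and 3 the gain is 10 / 33 / 18%. At d = 0.68, the effect implied by N = 92 for a single coefficient, power with 55 per arm is 94% for Model 2, 85 / 94 / 99.5% for Model 3 and 96 / 98 / 99.9% with T1 adjustment. The gain over the better model is then about 0.4 to 4 points. At ρ near 0, adjustment costs about 1% in variance at this sample size, so the statement that it never loses holds only apart from that lost degree of freedom.

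The disagreement rates assume that pairing is respected in Model 3, which the SAP does not say, so they are illustrative. None of these points supplies the missing decision rule.

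**Conclusion.** The concern holds. Neither document names a deciding Hypothesis 1 model, and T1 adherence is a covariate in none of the three. Bias is not at issue, and the trial is not invalidated. The missing rule matters at any correlation: Models 2 and 3 disagree in 26-34% of trials at d = 0.5 and 9-24% at d = 0.65, and accepting either raises the false-positive rate to about 9%. The direction of the precision gain needs no assumed correlation. Its size does, and it rests on the assumed d and ρ, equal SDs, a normal outcome and a paired Model 3. It is small if the effect is large, if ρ is low (against Model 2) or if ρ is high (against Model 3). Because the ranking of Models 2 and 3 turns on an unknown ρ, choosing between them is a guess that T1 adjustment avoids. This should be changed before the data are analysed.

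**What to change.** In the SAP under Hypothesis 1, name one primary analysis: linear regression of 12-week adherence on treatment, T1 adherence, age, education and income. Judge Hypothesis 1 only on the treatment coefficient at two-sided 0.05. Label Models 1, 2 and 3 supportive. Fix this covariate set in advance and exempt it from the r > 0.4 selection rule, which could otherwise change the primary model after the data are seen. The primary outcome description need not conflict with this: with T1 in the model, regressing the T1-T2 change or the T2 value gives the same treatment coefficient. One sentence in Measures can say so.

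Align the power statement in the SAP and in section 8.0 of the protocol: list the five predictors, the coefficient tested and the assumed effect size.

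The cost is wording and one degree of freedom (87 to 86 at N = 92, with income as a single score). T1 adherence is already collected. If N = 92 was set for a single coefficient, a fifth predictor at the same f² = 0.117 leaves power at 90.0%. If it was set for the overall test, a fifth predictor with f² unchanged at 0.177 gives 87% and would need N = 99. That is a worst case, because it credits T1 adherence with no explanatory value, and the overall test is not the test of Hypothesis 1.

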5.0 Study Procedures

The proposed study will include 2 zoom focus groups of 6-8 individuals each (or zoom interviews with the same number of individuals), which will solicit feedback on text messages and the usability of the prototype app and be approximately 2 hours long, and a randomized control trial (RCT) to evaluate the effectiveness of the DOT intervention on PrEP adherence among young adult MSM on PrEP. For the RCT, those who meet study criteria will complete online baselines in Qualtrics, then be randomized by Qualtrics to either the intervention group (DOT mobile app) or the control group (2page document offering PrEP adherence education).

Study procedures:

Formative Focus Groups/Interviews: After signing an online informed consent form, individuals will meet together for a 2 hour conversation (either in a focus group or interview), during which they will provide feedback on new text messages and the usability of the prototype app. Focus groups will be audiotaped. Participants will receive a \$75 Amazon gift card at the end of the focus group.

RCT (both arms): Those who consent to the RCT will automatically receive a link to collect demographic data, e.g. age, ethnicity, education, income, and length of time on PrEP, and the baseline assessments. Qualtrics will then randomize participants to the intervention or control arm. Intervention and control participants will be offered a \$20 Amazon gift card for completing baselines. At study completion (12 weeks), all participants will receive a text and email informing them that it is time to re-take baseline assessments. After completion, they will receive a \$155 Amazon gift card.

RCT Intervention Group: Intervention participants will receive a link to download the DOT mobile app from our website. During the 12-week study period, intervention participants will receive 3 types of messages: pill reminders, educational, and motivational (including new ones targeting stress). The

Protocol #2 R44 MH112221-02

Version: 3

November 23, 2020

DOT app will also include a link to the DOT online community (with online community rules that each participant must agree to before become a part of the community) and a “GET HELP NOW” link to the federal crisis intervention program. We have attached the online community rules for IRB review.

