Perceived stress burden will be included as a potential mediating variable for two reasons: First, the intervention targets stress burden via supportive texts and an online community. Second, reductions in perceived stress can facilitate medication adherence (Stewart et al., 2005). Stress burden will be assessed using the 10-item **Perceived Stress Scale** (Cohen et al., 1983), which has been validated with a wide-range of patient and non-patient groups (e.g. Chiu et al., 2016; Perera et al., 2017). We will analyze psychometric properties and construct validity on the two new measures (intention to follow guidelines and PrEP knowledge) as a part of our Phase 2 analyses.

Moderating Variable. Length of time on PrEP (in months) will be included as a moderator as it seems possible that the greater the length of time on PrEP, the more likely a participant has developed personal strategies to support adherence or have supports (family members, friends, healthcare providers) in his social environment that help with adherence.

Demographic and Control Variables. T1 assessments will also gather a number of demographic indicators, including age, years of education, income and, as mentioned above, length of time on PrEP. Income will be coded categorically from 1 to 7 in relation to the federal poverty level: <100% (1), 100%-149% (2),

150%-199% (3), 200%-249% (4), 250%-299% (5),
300%-349% (6), 350%-399% (7), and $\geq 400\%$.

Randomization: Participants will be randomly assigned to intervention or control group via the randomizer function on Qualtrics software. **Sample size:** We will aim to recruit and gain consent from 110 participants (55 each for intervention and control arms). **Power analysis:** Based on our Phase 1 pretest results, an a priori power analysis for a multiple regression with 4 predictors of PrEP adherence was conducted to determine a sample size with a power of at least 90% with a two-sided alpha level of .05. The desired minimum sample size was 92 participants (Rosner, 2010). In the event of 20% attrition, we added 20% additional participants to the sample, and set 110 as the total sample size. Therefore, even if the study encounters diminished recruitment or greater post-recruitment attrition, it should still be possible to detect moderate effects.

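### The adjusted Hypothesis 1 model omits T1 adherence, and Model 3 uses it only through a less precise change contrast; adjusting for it would gain precision at almost no cost

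*SAP*

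**What the plan says.** The SAP (Hypothesis 1) sets out three linear regressions. Model 1 contains arm only. Then "the second regression model will add three confounders (three demographic variables: age, education, and income". Then, "besides the 3 confounders, the third regression model will add an interaction term", built from arm, a before/after indicator and their product; the product term is read as the difference between arms in the increase in adherence.

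Under Primary outcome measure, the SAP defines the outcome as the T1-to-T2 difference in a three-item self-report adherence measure, taken at both times. Protocol 5.0 has participants complete baseline before Qualtrics randomises them, and the data collected then cover "age, ethnicity, education, income, and length of time on PrEP, and the baseline assessments". T1 adherence is therefore a true pre-randomisation value. The SAP's analysis set is everyone who consents and engages in the T1 assessment.

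Length of time on PrEP is listed under Demographic and Control Variables, among "demographic indicators, including age, years of education, income and, as mentioned above, length of time on PrEP", but is in none of the three models. Its assigned role is different: "Length of time on PrEP (in months) will be included as a moderator as it seems possible". It is then examined under Hypothesis 2, in moderation and moderated mediation.

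**The concern.** The baseline value of an outcome is usually its best single predictor. Model 2 adjusts for three demographic variables and leaves that value out, so whatever part of T2 adherence T1 adherence explains stays in the error term. The arm contrast also carries any chance difference in T1 adherence. Neither document states any stratification, and the SAP's Analysis plan only tests T1 differences between arms and discusses those that are significant, which adjusts nothing.

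Model 3 subtracts the T1 difference in full, where baseline adjustment subtracts only the part that carries over to T2. What is at stake is the width of the confidence interval for the main comparison in a trial of 110 people.

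**Working it through.** **The plan's own figures.** The step to 110 reproduces: 92 × 1.2 = 110.4. The 92 cannot be reproduced, because no numerical effect size is given. Power of 90% at 92 back-solves to f² = 0.177 for the overall 4-df test, or f² = 0.117 (standardised difference about 0.68) for a single coefficient. The conventional f² = 0.15 gives 108 or 73. The four predictors are not named; arm plus three confounders fits Model 2. So nothing shows that the calculation took credit for T1 adherence.

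**Variance of the three contrasts.** Let ρ be the T1–T2 correlation given arm, age, education and income, and assume equal variances at T1 and T2. In units of the post-test variance:

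- post-test only (Model 2): 1
- change (Model 3 interaction): 2(1 − ρ)
- baseline-adjusted: 1 − ρ²

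The equivalent sample size for the adjusted analysis of 110 is 110/(1 − ρ²) against the post-test. Against change it is 110 × 2(1 − ρ)/(1 − ρ²) = 110 × 2/(1 + ρ). The documents give no ρ, so a range is assumed.

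| ρ (assumed) | Post-test | Change | Adjusted | Equivalent N vs post-test | Equivalent N vs change |
|---|---|---|---|---|---|
| 0.3 | 1 | 1.40 | 0.91 | 121 | 169 |
| 0.5 | 1 | 1.00 | 0.75 | 147 | 147 |
| 0.7 | 1 | 0.60 | 0.51 | 216 | 129 |

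At ρ = 0.5, allowing for the lost degree of freedom at N = 110, the standard error ratio against Model 2 is √(0.75 × 105/104) = 0.870. For an assumed standardised difference of 0.5, power at N = 110 moves from 73.8% to 85.1%; at ρ = 0.3 it moves to 77.7%.

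**The same thing as chance imbalance.** With 55 per arm, the 95% range for a baseline difference is ±1.96 × 2/√110 = ±0.37 SD. If half of it carries over (ρ = 0.5), Model 2 can be shifted by 0.5 × 0.37 = 0.19 SD. Model 3 removes all of it instead of half, and so errs by the same 0.19 SD the other way.

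**Length of time on PrEP.** Added to Model 2, the standard error ratio is √[(1 − r²)(N − 5)/(N − 6)], with r its assumed partial correlation with T2 adherence. At N = 88 (110 less 20%):

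- r = 0.1: 1.001, no gain
- r = 0.2: 0.986, a fall of about 1.4%
- r = 0.4: 0.922, a fall of about 8%

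**Simulation.** 1,500 trials of 92 were run without age, education and income, with T1–T2 correlation 0.5 given time on PrEP. Empirical SDs of the arm estimate:

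| Analysis | r = 0.2 | r = 0.4 |
|---|---|---|
| Post-test | 0.203 | 0.210 |
| Post-test + time on PrEP | 0.203 | 0.192 |
| Model 3 interaction | 0.204 | 0.191 |
| T1-adjusted | 0.178 | 0.172 |
| T1-adjusted + time on PrEP | 0.179 | 0.167 |

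At r = 0.4 the overall T1–T2 correlation is 0.16 + 0.84 × 0.5 = 0.58, so theory gives an SD ratio of √(1 − 0.58²) = 0.81 against the post-test; the simulation gives 0.172/0.210 = 0.82. Adding time on PrEP to Model 3 as a main effect left the interaction estimate identical, with the same true SD.

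**The case against.** The strongest reply is Model 3. The primary outcome is defined as a T1–T2 difference, the Model 3 interaction estimates exactly that, and T1 adherence enters as the before measurement. It would be wrong to infer that Hypothesis 1 ignores T1 adherence. It stands, too, that an imbalance acting equally at T1 and T2 cancels in Model 3. But the change contrast pays for this in variance: 2(1 − ρ) exceeds 1 − ρ² for every ρ below 1 when the variances are equal. Under randomisation the adjusted T2 difference and the difference in change have the same target, so nothing in the outcome definition requires the less precise form.

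A second reply is that the covariate set is explicit, fits the four predictors of the power analysis, and is unbiased by design. That also stands. A reader might infer that the omission biases the treatment effect; random allocation rules out systematic bias.

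A reader might also infer that the SAP argues time on PrEP drives adherence and then discards it, losing precision for free. The documents do not support this. The SAP's reasoning, that "the greater the length of time on PrEP, the more likely a participant has developed personal strategies to support adherence", is introduced only as something that seems possible, and it is offered to justify moderation. No correlation is given, the likely gain is small, and a covariate does cost a degree of freedom. The variable also has a stated use under Hypothesis 2, whose first regression arguably already includes it among the demographic variables.

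**Conclusion.** The point holds as a matter of precision, and it rests mainly on T1 adherence. At an assumed T1–T2 correlation of 0.5 with similar variances, baseline adjustment cuts variance by about 25% against both Model 2 and the Model 3 contrast, equivalent to about 147 participants instead of 110. A higher correlation enlarges the gain over Model 2 and shrinks the gain over Model 3; a lower one does the reverse. Time on PrEP is a minor addition: about nil to 1.4% of the standard error at assumed partial correlations of 0.1 to 0.2, and no real gain in Model 3. All correlations are assumptions. The change is worth making, but the planned models are not invalid without it. Nor does this show that the trial is underpowered, since the effect size behind 92 is not stated.

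**What to change.** In the SAP (Hypothesis 1), before outcome data are examined, specify the adjusted model as T2 adherence on arm, T1 adherence, age, education and income. Length of time on PrEP in months may be added as a further prespecified covariate; if it is not, one sentence should say why it serves only as a moderator. Models 1 and 3 can stay as supporting analyses.

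Two consequential edits follow. State that these covariates are fixed in advance and exempt from the SAP's rule of dropping one of two similar variables correlated above 0.4. Include them in the imputation model for missing T2 values.

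The cost is one degree of freedom per covariate and an update to the four-predictor wording in the SAP (Power analysis) and Protocol 8.0: five predictors, or six with time on PrEP. No new data are needed.

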Measures. Both baseline (T1) and 12-week follow up (T2) data will be collected on the following key measures: **Primary outcome measure:** The primary outcome compares differences between (T1) and (T2) for the key measure of interest: PrEP adherence: Our Phase 1 open-ended data revealed participants' general discomfort with blood tests and needles. Thus, we will not seek PrEP blood levels in Phase 2 to measure adherence as doing so would likely pose a barrier to recruitment and retention. Instead, we will use Wilson's simple 3-item self-report adherence measure which showed good psychometric characteristics and good construct validity when compared with an electronic drug monitoring standard, for both HIV and non-HIV medications, and has been validated with culturally-diverse patient groups, including MSM (Fowler et al., 2014; Wilson et al., 2014; 2016). The items include: 1) In the last 30 days, on how many days did you miss at least one dose of any of PrEP (write in # of days) 2) In the last 30 days, how good a job did you do at taking your PrEP in the way you were supposed to? (6-point Likert) 3) In the last 30 days, how often did you take your PrEP in the way you were supposed to? (6-point Likert). Note: We will also examine self-report app adherence data. App adherence data can only be collected via the app as yes or no responses to pill reminders, and thus cannot serve as pre-intervention baseline. We will, however, compare app adherence data from weeks 1 and 12.

Consideration of Relevant Biological Variables: We will only include culturally-diverse young adult males who have sex with other males in our study as they are disproportionately represented among groups at increased risk for HIV. Moreover, males account for 95.3% of all PrEP users (Huang et al., 2018).

Mediating Variables: We propose four mediating variables: PrEP self-efficacy, intention to follow PrEP guidelines, PrEP knowledge and stress burden. To measure PrEP treatment self-efficacy, we will use the **Adherence Self-Efficacy Scale** (ASES) (Johnson et al., 2007). It is a 12-item scale of patients' confidence to carry out

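### In Model 3 age, education and income enter only as main effects, so the treatment-by-time estimate is exactly the unadjusted difference in mean change

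*SAP*

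**What the plan says.** The SAP, under Hypothesis 1, sets out three linear regressions of PrEP adherence.

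- Model 1 compares the arms after 12 weeks, with treatment as the only term.
- Model 2 will "add three confounders (three demographic variables: age, education, and income"), and its purpose is "to compare the gaps after controlling for age, education and income level".
- Model 3 builds on Model 2: "besides the 3 confounders, the third regression model will add an interaction term, the dichotomous treatment variable and the dichotomous intervention variable". The last of these variables is time, T1 against T2. The model is read as follows: "The coefficient of the interaction term will be the difference between the increase in intervention group and the increase in control group".

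Treatment by time is the only interaction named. No demographic-by-time term appears.

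Three further statements in the SAP fix the data layout.

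- On the covariates (Demographic and Control Variables): "T1 assessments will also gather a number of demographic indicators, including age, years of education, income".
- On the outcome (Measures): "Both baseline (T1) and 12-week follow up (T2) data will be collected on the following key measures".
- On dropout (Data Analysis): "Data will be imputed using multiple imputation for participants who fail to complete the T2 (posttest) assessment".

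Protocol section 5.0 agrees. It lists the demographic questions separately from the baseline assessments, and only the assessments are repeated at 12 weeks.

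**The concern.** The SAP defines the primary outcome as a T1 to T2 comparison, and Hypothesis 1 is about improvement. Model 3 is the only one of the three models that addresses change. It carries forward three variables that the SAP calls confounders, and the evident reason is to keep controlling for them. For the coefficient that tests improvement, they do nothing.

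Two things are at stake. First, if the arms differ by chance on a covariate that predicts change, Model 3 leaves that difference in the estimate, and a reader may think it has been dealt with. Second, the p-value in stacked ordinary regression does move when the covariates are added, which gives the appearance that an adjustment took place.

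**Working it through.** **Inputs.** Model 3 terms: treatment, time, treatment by time, age, education, income (SAP, Hypothesis 1). Covariates measured at T1 only (SAP, Demographic and Control Variables). One T1 row and one T2 row per man after imputation (SAP, Data Analysis). Planned size 110, 55 per arm (SAP, Sample size); 92 × 1.20 = 110.4 reproduces the 110. The plan gives no figure for the Model 3 effect or its standard error.

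**Step 1: the estimate.** Let t be treatment (0/1) with mean m, and s be time (0 = T1, 1 = T2).

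- Regress t·s on intercept, t and s. The residual is r = (t − m)(s − 1/2), because t·s − r = t/2 + m·s − m/2, which is linear in t and s.
- Within a man, r is −(t − m)/2 at T1 and +(t − m)/2 at T2. For any covariate x that is the same on both rows, x·r sums to zero over the two rows. So r is orthogonal to age, education and income, however prognostic or imbalanced they are and however income is coded.
- The coefficient is Σr·y / Σr² = Σ(t − m)·d / Σ(t − m)², with d the T2 minus T1 change. This is the difference in mean change between arms.
- It holds in each imputed data set, and so for the pooled estimate.

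Numerical check on assumed data (500 data sets per layout, covariates prognostic for level and change and imbalanced between arms): the largest difference in the coefficient with versus without covariates was 2e-14 at 55:55 and 5e-14 at 60:50.

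**Step 2: the printed standard error.** In stacked ordinary regression SE = residual SD / √Σr². With 55:55, r = ±1/4 on all 220 rows, so Σr² = 220/16 = 13.75 with or without covariates. Only the residual SD changes. In 400 further data sets at 55:55 (assumed data):

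| Quantity | Without covariates | With covariates |
|---|---|---|
| Ordinary-regression SE (mean) | 0.454 | 0.383 |

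The true sampling SD of the estimate, which is one and the same in both fits, was 0.272. The mean clustered SEs of the two fits were 0.279 and 0.281, practically equal and close to that value. Significance at 0.05 under ordinary regression changed in 13% of the data sets although the estimate did not. A random-intercept fit (one data set each at 55:55 and 60:50) left both estimate and SE unchanged to five decimals.

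**Step 3: what real adjustment would do.** Let R² be the share of the variance of change explained by the k = 3 covariates. The documents give no value, so 0 to 20% is an assumed range. Allowing for the cost of fitting three roughly normal covariates in n = 110 men,

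SE ratio = √[(1 − R²)(n − 3)/(n − 3 − k)] = √[(1 − R²) × 107/104].

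| R² | SE ratio | Change in SE |
|---|---|---|
| 0 | √1.0288 = 1.014 | +1.4% |
| 5% | √0.9774 = 0.989 | about −1% |
| 10% | √0.9260 = 0.962 | about −4% |
| 20% | √0.8231 = 0.907 | about −9% |

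Simulated change-score regressions (6,000 data sets per value) gave 0.989, 0.963 and 0.908 for R² of 5%, 10% and 20%. Inverting and squaring those ratios, the gain is worth about 2%, 8% and 21% more men. Break-even is R² = 1 − 104/107 = 2.8%.

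**Step 4: the two ways to adjust.** Regressing change on treatment plus covariates and adding covariate-by-time products to Model 3 give the same point estimate. Their standard errors differ if the stacked rows are treated as independent. In one assumed correlation structure, adding the products to ordinary regression raised the mean SE from 0.285 to 0.289 (R² = 5%) and from 0.283 to 0.285 (R² = 10%), while the change-score SE was about 0.19.

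**The case against.** The strongest reply is that nothing in Model 3 is wrong. The SAP never calls its coefficient adjusted: the phrase about controlling for the demographics belongs to Model 2, which does adjust the 12-week comparison. Model 3's coefficient is described as the difference between the two arms' increases, which is what it estimates. A difference in changes already removes any constant effect of the covariates on adherence level. Only covariates that predict change could matter, and the SAP states no expectation that these three do. The gain from adjusting is small at the low end and slightly negative if they predict nothing.

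All of this stands, and it limits the point. It does not remove it: the covariates are in Model 3 by design, have no effect on its estimate, and do alter the ordinary-regression p-value.

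A reader might infer three stronger things.

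- That the estimate is biased. The documents do not support this: allocation is by the Qualtrics randomiser, so the unadjusted difference in change is unbiased in expectation with respect to these covariates.
- That the SAP misreports an unadjusted result as adjusted. It does not say so; that reading is only an inference from Model 3 building on Model 2.
- That covariate-by-time products alone would repair the model. They repair the estimate, but the SAP names no method for paired rows, so a valid standard error would still be lacking.

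**Conclusion.** The point holds. As specified, Model 3 returns the unadjusted difference in mean change, exactly, whatever the values of age, education and income. The fall in the ordinary-regression standard error when they are added is not a gain in precision.

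The consequence is modest: chance imbalance in covariates that predict change stays in the estimate, and a standard-error reduction of about 1% to 9% is forgone if they explain 5% to 20% of the variance of change. The downside of adjusting is about 1.4% if they explain nothing. Those percentages rest on the assumed R² range; the identity does not.

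The identity does require both rows for every man analysed. If dropouts' T1 rows were kept without an imputed T2 row, the coefficient could move: by 0.12 on average in a simulation with 20% covariate-related missingness and a true effect of 0.5. The planned imputation rules this out for the main analysis, and a completers-only analysis that uses both rows restores the identity.

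**What to change.** Replace Model 3 with a regression of the T2 minus T1 change in adherence on treatment, age, education and income. This has one row per man, so pairing is handled, and the treatment coefficient is the adjusted difference in improvement.

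If the stacked form is kept, add the products of the before/after variable with age, education and income, and name a method that accounts for the two rows per man, such as clustered standard errors or a suitable mixed model.

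If neither is done, add a sentence to the SAP saying that the Model 3 interaction is the unadjusted difference in change.

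The cost is a line or two of SAP text and three coefficients estimated from data already planned. No new data or participants are needed. It is best settled before outcome data are seen.
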